9.5 Pharmacokinetic/Pharmacodynamic Assessment

PK/PD modelling may be employed to characterize the exposure-response relationships between LY3478045 concentrations and various PD endpoints, provided enough data are available.

9.6 Safety and Tolerability Assessments

9.6.1 Adverse events

Where changes in severity are recorded in the Case Report Form (CRF), each separate severity of the adverse event (AE) will be reported in the listings, only the most severe will be used in the

summary tables. A pre-existing condition is defined as an AE that starts before the subject has provided written informed consent and is ongoing at consent. A non-treatment emergent AE is defined as an AE which starts after informed consent but prior to dosing. A treatment-emergent AE is defined as an AE which occurs postdose or which is present prior to dosing and becomes more severe postdose.

All AEs will be listed. Treatment-emergent AEs will be summarized by Part, treatment, severity and relationship to the study drug. The frequency (the number of AEs, the number of subjects experiencing an AE and the percentage of subjects experiencing an AE) of treatment-emergent AEs will be summarized by Part, treatment, Medical Dictionary for Regulatory Activities (MedDRA) version 22.1 system organ class and preferred term. The summary and frequency AE tables will be presented for all causalities and those considered related to the study drug by the investigator. Any serious AEs will be listed.

Discontinuations due to AEs will be listed.

9.6.2 Concomitant medication

Concomitant medication will be coded using the World Health Organization (WHO) drug dictionary (Version March 2019). Concomitant medication will be listed.

9.6.3 Clinical laboratory parameters

All clinical chemistry and hematology data will be summarized by parameter and treatment group together with changes from baseline, where baseline is defined as the Day 1 predose assessment, and listed. Urinalysis data will be listed. Additionally, clinical chemistry, hematology and urinalysis data outside the reference ranges will be listed and flagged on individual subject data listings.

9.6.4 Vital signs

Vital signs data will be summarized by Part and treatment group together with changes from baseline, where baseline is defined as the Day 1 predose assessment. Figures of mean vital signs and mean changes from baseline profiles will be presented by Part and treatment.

Values for individual subjects will be listed.

9.6.5 Electrocardiogram (ECG)

The ECG data will be obtained directly from the 12-lead ECG traces. These data include the PR, QT, RR, QRS duration and heart rate. In addition, QT interval corrected using Fridericia's formula (QTcF) will be calculated as follows:

$$QTcF = \frac{QT}{\sqrt[3]{\frac{60}{HR}}}$$

The mean of triplicate data will be used for reporting. The ECG data will be summarized by Part and treatment group together with changes from baseline, where baseline is defined as the mean of the triplicate Day 1 predose assessments (-1.5, -1 and 0.5 hours). Figures of mean ECG data and mean changes from baseline will be presented by Part and treatment. The frequency of subjects with a maximum increase from baseline in QTcF interval will be summarized for each treatment according to the following categories: >30 ms and >60 ms. In addition, the frequency of subjects QTcF postdose values, according to the following categories: >450 ms, >480 ms and >500 ms, will be summarized by Part and treatment.

Plasma PK Concentration versus delta and double delta ECG parameter analysis

A plasma LY3478045 concentration-ECG parameter analysis will be performed to assess the relationship between changes from baseline (mean of Day 1 predose triplicate assessments) in ECG parameters (QTc, PR, and RR intervals, QRS duration, and heart rate) and plasma LY3478045 concentrations across all treatments. The change from baseline adjustment will be based on individual subject's Day 1 predose value. Further details on how these will be calculated:

- Calculate the baseline ECG value for each subject, which is the mean of ECG parameter values of each individual subject over 3 predose time points at day 1.
- Calculate the change from baseline at each timepoint for each individual subject.

The relationship between LY3478045 concentrations and ECG parameters will be explored graphically by plotting delta ECG parameter values against LY3478045 concentrations, including all post dosing timepoints.

A mixed effects analysis model will be employed with change from baseline in ECG parameter as the dependent variable, LY3478045 concentration and baseline ECG parameter value as continuous covariates, treatment and time as categorical factors, and a random intercept and slope per subject. Treatment will be fitted as a binary variable (Placebo, or LY3478045). The model will have the form

$$\Delta ECG_{ijk} = (\theta_0 + \eta_{0,i}) + \theta_1 TRT_j + (\theta_2 + \eta_{2,i}) C_{ijk} + \theta_3 TIME_j + \theta_4 (ECG_{i,j=0} - \overline{ECG_0}) + \varepsilon_{ijk},$$

where ΔECG_{ijk} is the change from baseline in ECG parameter for subject i in treatment j at time k , θ_0 is the population mean intercept in the absence of treatment effect, $\eta_{0,i}$ is the random effect associated with the intercept term θ_0 , θ_1 is the fixed effect categorical variable associated with treatment TRT_j , θ_2 is the population mean slope of the assumed linear association between concentration and ΔECG_{ijk} , $\eta_{2,i}$ is the random effect associated with the slope θ_2 , C_{ijk} is the concentration for subject i in treatment j and time k , θ_3 is the fixed effect associated with time, θ_4 is the fixed effect associated with baseline $ECG_{i,j=0}$, $\overline{ECG_0}$ is the overall mean of $ECG_{i,j=0}$ (the mean of all the baseline ECG parameter values, at time 0), and ε_{ijk} is the residual error. It will be assumed the random effects are multivariate Gaussian distributed with mean vector 0 and an unstructured covariance matrix G , whereas the residuals, ε_{ijk} , are Gaussian distributed with mean 0 and variance r .

The predicted mean change from baseline and placebo-corrected change from baseline in ECG parameter (Δ ECG and $\Delta\Delta$ ECG respectively) at the observed geometric mean C_{max} of each treatment (slope estimate * C_{max} + treatment effect) and two-sided 90% CI at different dose levels will be calculated. Residual plots will be produced to assess the adequacy of the model.

Example of SAS code as follows:

```
proc mixed data=xxxx;
by param;
class treat time subject;
model  $\Delta$ ECG = treat time baseline_ECG PKconc / solution cl alpha=0.1 ddfm=kr;
random intercept PKconc / type=un subject=subject;
estimate 'XX mg LY3478045' intercept 1 treat 0 1 PKconc [cmax XXmg] / CL
alpha=0.1;
estimate 'YY mg LY3478045' intercept 1 treat 0 1 PKconc [cmax YYmg] / CL
alpha=0.1;
ods output solutionF=sol;
ods output estimates=estim;
run;
```

Similar code will be used for the analysis of $\Delta\Delta$ ECG.

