2.1. Part A (Single-Ascending Doses)

	Screening	Days							FU ^a	ED ^b	Comments
Procedure	^c ≤28 days before Day -1	-1	1	2	3	4	5	7	14		
Informed Consent	X										
Admission to CRU		X									
Discharge from CRU						X					Subjects may be discharged on Day 5 at the discretion of the investigator.
Non-Residential Visit							X	X	X	X	
LY3478045 Administration			X								
Medical History	X										Information regarding occasional use of vitamin/mineral supplements will be taken as a part of the medical history evaluation at the time of subject screening.
Complete Physical Examination	X								X	X	Targeted PE may be conducted at other visits at the discretion of the investigator.
Height	X										
Weight	X	X									
Pregnancy Test	X	X							X	X	Serum pregnancy test will be performed at screening and urine pregnancy test will be performed at all other specified timepoints.
Blood Pressure and Pulse Rate (Supine) ^c	X	X	P, every 1 h up to 12 h postdose	24, 36 h	48 h	72 h		X	X	X	
Body Temperature	X	X							X	X	
Clinical Laboratory Tests	X	X	P	X	X			X	X		See Appendix 2 for complete list.
Serum Creatinine ^d			P, 4, 12, 24 h								
TriPLICATE 12-Lead ECG			Predose: 1.5 h, 1 h, and 30 min. Postdose: 0.5, 1.5, 2.5, 4, 6, 8,	24 h							

	Screening	Days							FU ^a	ED ^b	Comments
Procedure	≤28 days before Day -1	-1	1	2	3	4	5	7	14		
			10, 12, 16 h								
Single 12-Lead ECG	X				X				X	X	
Adverse Event Recording	X	X	X	X	X	X	X	X	X	X	
Pharmacokinetic Sampling ^d			P, 0.75, 1.5, 3, 4, 6, 8, 10, 12, 16 h	24 h	48 h	72 h	96 h				
Meal (Low Fructose)			20 min, 6, 12 h								
Fructose Beverage (for Fructose Tolerance Test)			during meal: 20 min, 6, 12 h								
Fructose Tolerance Test Assay ^d			CCI	CCI							
Genetic Sample			X								
Fasting Biomarker Samples (Nonpharmacogenetic)		X		X							
CCI			P, 0.75, 1.5, 3, 4, 8, 12, 16 h	24 h	48 h	72 h	96 h				
24-hour Urine Collection for LY3478045 and Creatinine ^d			0-12, 12-24 h	24-36, 36-48 h	48-60, 60-72 h						

Abbreviations: CRU = clinical research unit; ECG = electrocardiogram; ED = early discontinuation; FU = follow-up; h = hour(s); min = minutes; P = predose; PE = physical examination.

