2.2. Part B (Cohorts 1 and 3; Multiple-Ascending Doses)

Procedure	Screening	Days										FU ^a	ED ^b	Comments
		-1	1	2	3 to 6	7	8	9 to 13	14	15 to 17	28			
Informed Consent	X													
Admission to CRU ^c		X												
Discharge from CRU											Day 17			
LY3478045 Administration						X								
Medical History	X													Information regarding occasional use of vitamin/mineral supplements will be taken as a part of the medical history evaluation at the time of subject screening.
Complete Physical Examination	X											X	X	Targeted PE may be conducted at other visits at the discretion of the investigator.
Height	X													
Weight	X	X									Day 15	X	X	
Pregnancy Test	X	X										X	X	Serum pregnancy test will be performed at screening and urine pregnancy test will be performed at all other specified

	Screening	Days										FU ^a	ED ^b	Comments
Procedure	≤28 days before Day -1	-1	1	2	3 to 6	7	8	9 to 13	14	15 to 17	28			
														timepoints.
Blood Pressure and Pulse Rate (Supine) ^c	X	X	P, every 1 h up to 12 h postdose	24, 36 h	48, 72 h				X		X	X		
Body Temperature	X	X										X	X	
Clinical Laboratory Tests (See Appendix 2)	X	X	P		Day 4	X			X		X	X		
Serum Creatinine			X			X			X					
Total Testosterone, Follicle-Stimulating Hormone, and Luteinizing Hormone	X		P	P							X	X	Samples will be collected early in the morning on Days 1 and 2, at the same time for both days, before or immediately after breakfast.	
Single 12-Lead ECG	X										X	X		
TriPLICATE 12-Lead ECG			Predose: 1.5 h, 1 h, and 30 min.						P, 0.5, 1.5, 2.5, 4, 6, 8, 12, 16 h	24 h				
Adverse Event Recording	X	X	X	X	X	X	X	X	X	X	X	X		
Pharmacokinetic Sampling ^d			P, 0.75, 1.5, 3, 4, 6, 8, 12, 16 h	24 h (predose)		P			P, 0.75, 1.5, 3, 4, 6, 8, 12, 16 h	24, 48, 72 h			Sampling times may be adjusted based upon review of interim PK	
Fasting Insulin and Adiponectin			P						P					
Meal (Low Fructose)			20 min, 6 h, 12 h						20 min, 6 h, 12 h					

Procedure	Screening ≤28 days before Day -1	Days										FU ^a	ED ^b	Comments
		-1	1	2	3 to 6	7	8	9 to 13	14	15 to 17	28			
Fructose Beverage (for Fructose Tolerance Test)			during meal: 20 min, 6, 12 h						during meal: 20 min, 6, 12 h					
Fructose Tolerance Test Assay ^d			CCI	CCI					CCI	CCI				
Genetic Sample		P												
Fasting Biomarker Samples (Nonpharmacogenetic)		X		X							Day 15			

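### The concentration–ECG model in SAP 9.6.5 has no Part or Day term and leaves TIME undefined; if the Parts are pooled by hour postdose, part of a Day 1 to Day 14 shift shared with placebo can enter the concentration slope

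*SAP*

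**What the plan says.** - **Data and model.** SAP 9.6.5 relates ECG changes to "plasma LY3478045 concentrations across all treatments". The model has concentration and baseline as covariates, plus "treatment and time as categorical factors, and a random intercept and slope per subject". Treatment is a two-level indicator, placebo or LY3478045.
- **Example code.** The class statement is "class treat time subject" and the right-hand side of the model is "treat time baseline_ECG PKconc / solution cl alpha=0.1 ddfm=kr". The procedure runs by ECG parameter only.
- **Baseline.** In both Parts it is the value "which is the mean of ECG parameter values of each individual subject over 3 predose time points at day 1".
- **ECG timing, Part A** (Protocol 2.1). Day 1: "Predose: 1.5 h, 1 h, and 30 min. Postdose: 0.5, 1.5, 2.5, 4, 6, 8", continuing to 16 h, with 24 h on Day 2.
- **ECG timing, Part B** (Protocol 2.2 and 2.3). Day 1 has predose triplicates only. On-treatment triplicates are on Day 14, "P, 0.5, 1.5, 2.5, 4, 6, 8, 12, 16 h", with 24 h on Day 15.
- **Reported quantity.** The change and the placebo-corrected change at each treatment's geometric mean Cmax (slope times Cmax, plus the treatment effect), with a 90% interval.
- **TIME.** Its levels are not listed. In the printed formula it carries the subscript that the legend assigns to treatment, not the one for time.

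**The concern.** In Part A the response is a same-day change. In Part B it is a change over 13 days of residence in the unit, on the unit's diet and under repeated procedures. Such a stay could move heart rate and the intervals in everyone, placebo included. For postdose triplicate ECGs, Part and Day are the same contrast, and the model as written has no term for it. Hour 1.5 on Day 1 and hour 1.5 on Day 14 would share one TIME level.

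Part B is also sampled after 14 once-daily doses, so its concentrations may be systematically higher. A shared rise could then look concentration-related, and a shared fall could hide a real effect. ECG change is part of the primary endpoint. Protocol 10.3.1.2 commits to a concentration-response analysis following ICH E14, and this is the only inferential ECG model in the SAP.

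**Working it through.** The SAP gives no effect size, SD or power for this analysis, so there is no figure to reproduce. The check asks what the written model would return if there were no drug effect.

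**Inputs from the documents**
- Part A: up to 5 cohorts of 6 active and 2 placebo, so 30 and 10. Part B: up to 4 such cohorts, so 24 and 8.
- ECG hours on each Part's profile: 10 in Part A (0.5 to 24 h) and 10 in Part B (predose to 24 h). Nine hours are common to both.
- Planned dose range 20–320 mg.

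**Assumptions, none from the documents**
- One-compartment PK with 30% between-subject variability; half-life 6, 12, 24 or 48 h.
- Part A at 20/40/80/160/320 mg, with several Part B dose sets.
- Between-subject SD about 0 to 8 ms and residual SD 5 to 7 ms across the runs. The 80–240 mg results below correspond to about 5 ms and 5–6 ms.
- A shift δ = 5 ms added equally to Part B active and placebo.

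**Step 1: where the leak arises.** Allocation is 3:1 in both Parts, so Part B makes up 24/54 = 44% of active and 8/18 = 44% of placebo subjects. On average the active-placebo contrast is not confounded with Part. The leak comes from concentration: if Part B active subjects sit higher on the concentration axis, the slope picks up δ. The treatment term then moves the other way to keep the average active-placebo difference near zero.

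**Step 2: expected estimate.** Let z = 1 for Part B records and 0 otherwise. The generalised least squares expectation is

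β = (X′V⁻¹X)⁻¹ X′V⁻¹ (δz),

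where X holds treatment, hour and concentration, and V the random-effect and residual variances. The baseline covariate is omitted because it is independent of the shift. The spurious placebo-corrected change is β(treatment) + β(concentration) × Cmax.

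**Step 3: results at the top Part B Cmax, δ = 5 ms, TIME as hours postdose**

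| Part B doses | Half-life | Spurious placebo-corrected change |
|---|---|---|
| 80–240 mg | 6 h | about 0.3 ms (0.3/5 = 6% of the shift) |
| 80–240 mg | 12 h | about 0.9 ms (18%) |
| 80–240 mg | 24 h | about 2.3 ms (46%) |
| top dose 300–320 mg | 6 to 48 h | 0.2 to 4.3 ms (4% to 86%) |
| top dose 150–160 mg | 6 to 12 h | −0.7 to 0.2 ms |

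The bias changes sign along the concentration axis. With Part B at 100/200/300/320 mg and a 24 h half-life, one run gives −1.3 ms at the 20 mg Part A Cmax and +2.6 ms at the top Part B Cmax. Where the top dose is 300–320 mg, the treatment term is biased by about −0.05 to −1.8 ms.

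**Step 4: fitted-model check.** 150 REML fits per scenario (random intercept only), Part B at 50/100/200/300 mg. The last two columns give the share of trials whose 90% lower bound exceeds zero; the nominal rate is 5%.

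| Half-life | Mean spurious change | As written | With Part, or day-by-hour TIME |
|---|---|---|---|
| 12 h | 0.77 ms | 8% | 3–4% |
| 24 h | 2.07 ms | 24% | 5% |

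The Monte Carlo standard error near 5% is √(0.05 × 0.95/150) = 1.8 points. The 12 h result is therefore barely distinguishable from nominal; the 24 h result is clear.

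**Step 5: the remedy.** With a Part term or day-by-hour TIME the spurious change is zero in the Step 2 calculation, and between −0.08 and 0.02 ms in the REML runs.

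**The case against.** The SAP never says that the Parts are pooled, and TIME could mean day-by-hour. Under either separate models or day-by-hour TIME the problem disappears. The missing BY-Part line in the code is weak evidence, because the example code also omits it for dose proportionality (9.3.1) and biomarkers (9.4.2), where the text says the Parts are analysed separately. This stands. Pooling is an inference, and it rests on the text: those sections state the separation and the Part B fructose model (9.4.3) names day, while this paragraph does neither.

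Everything that drives the size is assumed: the shift, the half-life, the Part B doses and the SDs. Exposure caps apply in both Parts, with the limits redacted, so how far Day 14 concentrations would exceed Day 1 concentrations cannot be checked. This also stands, and it is why only a range is given.

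There are partial safeguards. ECG summaries and mean-change figures are produced by Part and treatment, so a shift in Part B placebo would be visible, and residual plots are required. These could alert the analyst, but they do not correct the model estimate or its interval.

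**Conclusion.** The point holds in conditional form. As written, the model has no term for a Day 1 to Day 14 shift. If the Parts are pooled and TIME is hours postdose, some of that shift can be reported as a concentration effect. For a 5 ms shift with Part B at 80–240 mg, the reported quantity is off by about 0.3 to 2.3 ms over half-lives of 6 to 24 h. The error is larger with more accumulation or higher Part B doses, and negligible with a short half-life and a 160 mg ceiling. All of this rests on the assumed PK, doses, SDs and shift.

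Three stronger readings are tempting but not supported:
- **That placebo cannot correct any of the shift, so all of it is credited to drug.** Part B placebo and the random intercept absorb some of it.
- **That the error equals slope times Cmax.** A simulation of the 80–240 mg, 24 h case gives 3.6 ms for that product. The SAP also adds the treatment effect, which is biased the other way: 2.3 − 3.6 = about −1.3 ms.
- **That the false-positive rate at least doubles whenever drug accumulates.** For a nominal 10% slope test at a 24 h half-life and a 5 ms shift, simulation gave 36% with Part B at 80–240 mg but 17% at 40–160 mg. The SAP states no decision rule on the slope.

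This should be settled before analysis because the remedy is so cheap. The documents do not show that the result will be materially wrong.

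**What to change.** In SAP 9.6.5, do one of the following:
- define TIME as day-by-nominal-hour, so that Day 1 and Day 14 hours are separate levels;
- add Part as a fixed effect, for example `class treat part time subject; model dECG = treat part time(part) baseline_ECG PKconc`. One term serves for both Part and Day, because they coincide for postdose triplicates;
- if separate models are intended, say so and use `by part param`.

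Update the ESTIMATE statements to match. The rows for change from baseline need coefficients for the Part and time at which they are evaluated. In the placebo-corrected contrast a Part main effect cancels.

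**Cost.** A Part main effect uses one degree of freedom. Full day-by-hour TIME uses nine more than hours alone (10 + 10 = 20 levels against 20 − 9 = 11). The full design has about 72 × 10 = 720 postdose records. At fixed variance components the standard error of the placebo-corrected change rises by about 0 to 0.1 ms in the 80–240 mg scenarios, and by up to about 0.3 ms at a 48 h half-life. No new data are needed, since placebo ECGs are already scheduled on the same days in each Part.

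### SAP 9.6.5 gives one expression for both the predicted change from baseline and the placebo-corrected change, but it equals only the second; the example ESTIMATE also lacks time coefficients

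*SAP*

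**What the plan says.** SAP 9.6.5 models the change from baseline in each ECG parameter. The fixed terms are a binary treatment factor, time, LY3478045 concentration and baseline, with "treatment and time as categorical factors"; each subject has a random intercept and slope. In the equation, baseline enters as a deviation from its overall mean, described as "the mean of all the baseline ECG parameter values, at time 0".

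The SAP then promises two predictions at the geometric mean Cmax of each treatment, each with a two-sided 90% interval: "The predicted mean change from baseline and placebo-corrected change from baseline in ECG parameter". One bracketed expression serves both: "slope estimate * C_{max} + treatment effect".

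The example code declares "class treat time subject" as class effects. It fits "treat time baseline_ECG PKconc / solution cl alpha=0.1 ddfm=kr" and then writes "estimate 'XX mg LY3478045' intercept 1 treat 0 1 PKconc [cmax XXmg] / CL". No code is printed for the placebo-corrected change; the SAP says only "Similar code will be used for the analysis of" it.

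Protocol 9.5.1 does not plan to assay placebo subjects' samples. SAP 9.6.5 does not say what concentration these subjects receive in the model.

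**The concern.** Two different quantities are promised and one formula is given. The code does not settle which is meant: it contains an intercept that the formula lacks, and it leaves out a factor that the model contains. A programmer cannot follow both the formula and the code for the change from baseline.

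Protocol 10.3.1.2 commits to a concentration-response analysis in line with ICH E14, and this is the only model-based ECG analysis in the SAP. At stake is the column of predicted changes from baseline and its intervals. Depending on how the section is programmed, that column could hold the placebo-corrected value under another name, or a prediction whose time point nobody has chosen.

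**Working it through.** **Inputs.** The equation, class effects and ESTIMATE come from SAP 9.6.5. Placebo concentration C = 0 is an assumption that the SAP does not state. The equation prints the time term with the treatment index; I read it as time. The plan gives no numerical prediction to reproduce. Its 90% interval agrees with the code's alpha (1 - 0.90 = 0.10).

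**Step 1: the two predictions.** Write θ0 for the intercept, θ1 for treatment, θ2 for the slope, θ3(t) for time and θ4 for baseline. At mean baseline the θ4 term is zero.

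- Active at Cmax: θ0 + θ1 + θ2·Cmax + θ3(t). This is the change from baseline.
- Placebo at C = 0: θ0 + θ3(t).
- Difference: θ1 + θ2·Cmax. This is the placebo-corrected change, and it is the SAP's expression.

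The expression minus the change from baseline is -(θ0 + θ3(t)), which is minus the predicted placebo change. This is algebra and needs no data.

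**Step 2: size, by illustration.** The documents give no placebo change. All these values are assumed: θ0 = -2 ms, θ1 = 1 ms, θ2 = 0.002 ms per ng/mL, Cmax = 2,970 ng/mL, and ten time effects between 0 and -6 ms with mean -3.3 ms.

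- Placebo-corrected change: 1 + 0.002 × 2,970 = 6.94 ms.
- Placebo change, averaged over time: -2 - 3.3 = -5.30 ms.
- Change from baseline: 6.94 - 5.30 = 1.64 ms.

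Using the expression would report 6.94 ms instead of 1.64 ms. Fitting one simulated Part A data set built on these values (30 active, 10 placebo, 10 post-dose times, random intercept only) gave 8.54, -4.96 and 3.58 ms. The same identity holds: 3.58 - (-4.96) = 8.54. More generally, an assumed placebo change between -5 and +5 ms gives an error of up to 5 ms.

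**Step 3: is the ESTIMATE estimable?** Each row of the design has a 1 for the intercept, a single 1 among the treatment columns and a single 1 among the time columns. So in any estimable vector the treatment coefficients and the time coefficients must each sum to the intercept coefficient.

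| Vector | Intercept | Sum of treat | Sum of time | Estimable |
|---|---|---|---|---|
| Printed, time coefficients taken as zero | 1 | 1 | 0 | No |
| Printed plus equal time coefficients summing to 1 | 1 | 1 | 1 | Yes |
| Treatment difference plus PKconc at Cmax | 0 | 0 | 0 | Yes |

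A rank check agrees. With n time levels the design has 1 + 2 + n + 1 + 1 = n + 5 columns and rank n + 3. The levels used here are the post-dose times with an ECG and a PK sample at the same nominal time.

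| | Time levels | Columns | Rank | With printed vector | With equal time coefficients | With treatment difference |
|---|---|---|---|---|---|---|
| Part A | 8 | 13 | 11 | 12 | 11 | 11 |
| Part B, Day 14 | 7 | 12 | 10 | 11 | 10 | 10 |

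A rank that rises means not estimable. Adding the mean baseline to the printed vector leaves 12 and 11, and centring baseline changes nothing here. The printed vector also fails with all ten Part A ECG times in the model. The result does not depend on any PK or variance assumption.

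In the simulated fit, a solution that sets the last time level to zero returns 5.80 ms for the printed vector. That is the prediction at the last level only, not the time average of 3.58 ms.

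**Step 4: baseline.** The ESTIMATE gives baseline_ECG a coefficient of zero. If the variable is centred, this means the mean baseline, as the equation intends. If it is raw, it means a baseline of 0 ms. The code does not say which.

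**The case against.** The code is labelled an example and has placeholders, and SAP section 3 describes the document as guidance, with separate table shells. Because the ESTIMATE contains an intercept, the programmer evidently aims at the change from baseline, and the bracketed expression can be read as shorthand. This is fair and limits the consequence. It does not remove the fault: the text assigns one expression to two quantities, and the code that might correct the text leaves time undefined.

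A reader might infer that the analysis will yield no estimate, or a prediction at 0 ms. The documents do not support either as the expected outcome. They do not settle how the software fills the missing time coefficients. The 0 ms case needs coding against the SAP's own centred equation. It would also be conspicuous: in the illustration it gave 102.09 ms instead of 3.58 ms.

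A reader might also infer that the QT conclusion or the slope is compromised. It is not. The expression is correct for the placebo-corrected change once placebo concentration is 0, and the fitted model is the same whichever prediction is drawn from it.

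Finally, it is tempting to prescribe fixed time weights or to move ECG times to match the PK draws. The SAP does not fix which time levels enter the model. The 0.5 and 2.5 h ECGs have no same-time PK sample, and the Day 14 predose pair in Part B would make eight levels instead of seven. The weights must therefore follow the levels actually fitted. The schedule is a separate trade-off and is not needed to correct this section.

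**Conclusion.** The point stands as an error of wording and example code in SAP 9.6.5, with limited consequence. The expression is wrong for the change from baseline by the predicted placebo change, ms for ms. The documents give no value for that change, so the 5 ms figure and the illustration rest on assumptions. The algebra needs only placebo C = 0 and prediction at mean baseline. The estimability result needs only that time is a class effect and that its missing coefficients are read as zero.

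Not affected: the slope, the placebo-corrected expression, and the descriptive and categorical QTcF summaries. It would go too far to call the concentration-ECG analysis invalid.

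**What to change.** In SAP 9.6.5:

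1. Limit the bracketed expression to the placebo-corrected change, and state that placebo concentration is set to 0 because placebo samples are not assayed.
2. Define the change from baseline as intercept + treatment + slope × Cmax + the time effect averaged over the fitted time levels, at mean baseline. In the ESTIMATE, write equal time coefficients that sum to 1 over the levels actually in the model. State this as a rule, not as a fixed fraction.
3. Use the centred baseline in the code, or put the mean baseline in the ESTIMATE.
4. Print the placebo-corrected ESTIMATE: a treatment difference plus PKconc at Cmax, with no intercept, for example `treat -1 1 PKconc [Cmax]`, with the sign set by the order of the treatment levels.

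The cost is a few lines of text and code, with no change to data, procedures or the fitted model. It is best done before ECG and concentration data are merged for the model, because Protocol 10.3.5 has the sponsor team unblinded at the dose reviews.
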